7.5.2. Exclusion criteria

Subjects will not enter the study if any of the following exclusion criteria are fulfilled:

1. History of any clinically significant disease or disorder which, in the opinion of the Investigator, may either put the subject at risk because of participation in the study, or influence the results or the subject's ability to participate in the study.
2. History or presence of hepatic or renal disease, or any other condition known to interfere with absorption, distribution, metabolism, or excretion of drugs.

3. Any clinically significant illness, medical/surgical procedure, or trauma within 8 weeks of the first administration of IMP.
4. Any clinically significant chronic infection (i.e., osteomyelitis, bronchiectasis, etc.) within 8 weeks prior to screening (chronic fungal nail infections are allowed).
5. Any infection requiring hospitalization or treatment with IV anti-infectives not completed at least 4 weeks prior to screening.
6. Any infection requiring oral anti-infectives (including antivirals) within 2 weeks prior to Day 1.
7. History of cancer, apart from squamous or basal cell carcinoma of the skin treated with documented success of curative therapy ≥ 3 months prior to dosing.
8. Any clinically significant abnormalities in clinical chemistry, hematology, or urinalysis results at screening and Check-in, as judged by the investigator, including:
 - Aspartate aminotransferase (AST) $> 1.0 \times$ upper limit of normal (ULN);
 - Alanine aminotransferase (ALT) $> 1.0 \times$ ULN;
 - Total bilirubin $> ULN$ (unless due to Gilbert' s syndrome);
 - Serum creatinine $> ULN$ at clinical laboratory;
 - Neutrophil count $<$ lower limit of normal (LLN);
 - Platelet count $< LLN$; and
 - Hemoglobin $< LLN$.
- Note: Abnormal screening laboratory tests may be repeated ONCE on a separate sample before subject is declared a screen failure.*
9. Any clinically significant abnormal findings in vital signs at screening and Check-in, as judged by the investigator.
10. Any clinically significant abnormalities on 12-lead ECG at screening and Check-in, as judged by the investigator.
11. Known history of a primary immunodeficiency or an underlying condition such as human immunodeficiency virus (HIV) infection or splenectomy that predisposes the subject to infection.
12. Any positive result on screening for serum hepatitis B surface antigen (HBsAg), hepatitis B core total antibodies, hepatitis C antibody and HIV antibody.

13. Known or suspected history of drug abuse within 1 year of dosing, as judged by the investigator.
14. Any severe herpes infection at any time prior to dosing, including, but not limited to, disseminated herpes (ever), herpes encephalitis (ever), recurrent *herpes zoster* (defined as 2 episodes within 2 years) or ophthalmic herpes (ever).
15. Any *herpes zoster* infection that has not completely resolved within 12 weeks prior to screening.
16. Opportunistic infection requiring hospitalization or parenteral antimicrobial treatment within 3 years of randomization.
17. Has received another new chemical entity (defined as a compound which has not been approved for marketing) within 4 weeks or 5 half-lives of administration of IMP in this study.
Note: Subjects consented and screened, but not randomized in this study or a previous phase I study, are not excluded.
18. Spontaneous or induced abortion, still or live birth, or pregnancy \leq 4 weeks prior to screening (females only).
19. Plasma/serum donation within 1 month of screening or any blood donation/loss more than 500 mL during the 3 months prior to screening.
20. Previous receipt of:
 - Anifrolumab;
 - B cell-depleting therapy (including but not limited to epratuzumab, ocrelizumab, or rituximab) \leq 52 weeks prior to screening.
21. History of severe allergy/hypersensitivity or ongoing allergy/hypersensitivity, as judged by the investigator or history of hypersensitivity to drugs with a similar chemical structure or class to anifrolumab or to any human gamma globulin therapy.
22. Any live or attenuated vaccine within 8 weeks prior to screening (administration of killed vaccines is acceptable, the Sponsor recommends investigator to ask if subjects are up-to-date on required vaccinations, including influenza [inactivated/recombinant] vaccine prior to study entry) (up-to-date vaccinations are recommended but not required for study participation).
23. Receipt of Bacillus Calmette-Guerin (BCG) vaccine within 1 year of screening.

24. Positive screen for drugs of abuse and positive screen for alcohol at screening and on admission to the study center.
25. Known or suspected history of alcohol or drug abuse or excessive intake of alcohol as judged by the investigator.
26. Use of any prescribed or non-prescribed medication including antacids, analgesics (other than paracetamol/acetaminophen), herbal remedies, megadose vitamins (intake of 20 to 600 times the recommended daily dose) and minerals during the 2 weeks prior to the administration of IMP or longer if the medication has a long half-life.

Note: Hormonal replacement therapy is allowed for females.

27. Involvement of any AstraZeneca, PAREXEL or study site employee or their close relatives.
28. Judgment by the investigator that the subject should not participate in the study if they have any ongoing or recent (i.e., during the screening period) minor medical complaints that may interfere with the interpretation of study data or are considered unlikely to comply with study procedures, restrictions and requirements.
29. Vulnerable subjects, e.g., kept in detention, protected adults under guardianship, trusteeship, or committed to an institution by governmental or juridical order.
30. History of vasculitis.

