7.5. Selection of Study Population

The investigator should keep a subject screening log of all potential subjects who consented and were subjected to screening procedures.

Subjects who fail to meet the inclusion criteria or meet any exclusion criterion should not, under any circumstances, be randomized into the study. There can be no exceptions to this rule.

This study will be conducted in male and female subjects.

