11.11.5. Laboratory assessments

Hematology and clinical chemistry values will be listed by subject and time point including changes from baseline and repeat/unscheduled measurements. Summary tabulations will be presented by treatment and time point for the safety analysis set. The baseline for the measurements will be the last pre-dose assessment performed on Day -1. Changes from

baseline will be calculated and presented for all post-baseline time points. Shift tables will also be presented.

The listings will include the following information: test name, date of measurement, reference range, result and flags for any measurements that are outside the reference range (e.g., AstraZeneca, program, or laboratory ranges).

Additional listings will be presented for the following:

- Urinalysis (macroscopic and microscopic, if applicable)
- Pregnancy testing (including FSH)
- QuantiFERON-TB GOLD testing
- Pap smear

The results of the viral serology, drugs of abuse screen, and alcohol screen will not be listed in the CSR.

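### Exclusion criterion 24, read literally, is met only when the drug and alcohol screens are both positive at both visits, so one positive screen does not exclude

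*Protocol*

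**What the plan says.** Exclusion 24 in Protocol section 7.5.2 is "Positive screen for drugs of abuse and positive screen for alcohol at screening and on admission to the study center". The list it belongs to opens with "Subjects will not enter the study if any of the following exclusion criteria are fulfilled", and section 7.5 makes the list binding: "Subjects who fail to meet the inclusion criteria or meet any exclusion criterion should not, under any circumstances, be randomized into the study". The next sentences of section 7.5 rule out exceptions.

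Three other places bear on how the screens are meant to be used:

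- **Table 1 (section 7.2)** marks the urinary drug screen, the serum alcohol screen and the inclusion/exclusion check at Visit 1 (screening) and again on Day -1.
- **Section 9.3** lists urine drugs of abuse and serum alcohol among the assessments made for eligibility.
- **Section 8.9.1** places randomization on the morning of dosing, so Day -1 is the last scheduled eligibility check before it.

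Three further exclusions touch the same ground. Numbers 13 and 25 concern known or suspected drug or alcohol abuse, or excessive alcohol intake, as the investigator judges. Number 28 lets the investigator exclude someone thought unlikely to comply with study requirements.

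**The concern.** An exclusion criterion built on objective tests should say which result excludes. As worded, number 24 describes a volunteer who fails both tests twice. A volunteer positive for one drug at screening and negative on everything else does not fit that description. Nor does one whose only positive result is alcohol on admission.

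Because section 7.5 allows no exceptions, the wording of each criterion carries weight later:

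- Section 7.5.5 ties withdrawal before dosing, and the replacement decision after dosing, to whether the subject meets the selection criteria.
- Section 11.5 counts departures from the inclusion and exclusion criteria as protocol deviations, which are discussed before database lock to define the analysis sets.
- Section 11.11.5 states that the drug and alcohol screen results will not be listed in the clinical study report. A reader of the report could not see from the listings whether anyone with a positive screen had been dosed.

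**Working it through.** The point is one of wording. No figure in the plan depends on it, so there is none to reproduce. The check sets the passages side by side.

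**1. The literal condition.** Let D1 and A1 be a positive drug and a positive alcohol screen at screening, and D2 and A2 the same on admission. With both conjunctions taken at face value, exclusion 24 is met when

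D1 and A1 and D2 and A2

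all hold. The purpose shown in Table 1 and section 9.3 corresponds to

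D1 or A1 or D2 or A2.

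The two conditions agree only when all four results are positive or all four are negative. With any mixture, the literal rule lets the volunteer in and the evident rule keeps the volunteer out.

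**2. Does the lead-in repair it?** No. "Subjects will not enter the study if any of the following exclusion criteria are fulfilled" says that one criterion is enough. It does not say how the parts inside a single criterion combine.

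**3. Comparison with exclusion 12.** That item begins "Any positive result on screening for serum hepatitis B surface antigen (HBsAg" and continues with a list ending in 'and'. The opening word 'Any' makes each item sufficient alone. Exclusion 24 has no such word.

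**4. Comparison with inclusion 3 (section 7.5.1).** A negative pregnancy test is required at screening and on admission. There 'and' is correct, because both results must be negative for entry. Exclusion 24 uses the same construction for a positive result that bars entry, and 'and' then has the opposite effect: it relaxes the rule.

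**5. Comparison with Table 1.** A condition that needs results from both visits cannot be met at screening. Table 1 nevertheless has eligibility checked at screening, with both tests done there. On the literal reading, that check could never exclude anyone under number 24.

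**6. Do other criteria close the gap?** Partly. Numbers 13 and 25 can be invoked if the investigator takes a positive result as grounds to suspect abuse or excessive intake. Number 28 can be invoked if the investigator takes it as a sign of poor compliance, for example with the 72-hour alcohol abstinence before admission in section 7.4. All three require a judgment. A single positive alcohol result on admission is not by itself a history of abuse.

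**The case against.** The strongest reply is that nobody would read the criterion this way. Section 7.5.2 often uses 'and' simply to list items: exclusion 12 does, and so do the laboratory limits under exclusion 8. Table 1 and section 9.3 make the intent plain, and an investigator faced with a positive drug screen has numbers 13, 25 and 28 to rely on.

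Much of this stands. The intent is clear, an experienced unit would probably act on it, and the practical effect is likely to be small. What does not stand is the parallel with exclusions 8 and 12, since both lists sit under an opening 'Any' that number 24 lacks. Falling back on judgment also gives up what an objective screen is for.

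A reader might infer more than the text supports in three ways:

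- **That exclusions 8, 9 and 10 share the fault**, because they too say 'at screening and Check-in'. They do not. Each opens with 'Any'; number 8, for instance, begins "Any clinically significant abnormalities in clinical chemistry, hematology, or urinalysis results at screening and Check-in, as judged by the investigator". That naturally covers a finding at either visit. The note to number 8 confirms it: "Abnormal screening laboratory tests may be repeated ONCE on a separate sample before subject is declared a screen failure" treats an abnormal screening test alone as leading to screen failure. The note is silent on repeating a Check-in sample, but that is only missing detail. It does not forbid a repeat, and section 11.2 already says which value is used when a measurement is repeated before dosing.
- **That laboratory baselines would be distorted**, since "The baseline for the measurements will be the last pre-dose assessment performed on Day -1". That argument needs exclusion 8 to admit subjects with out-of-range Day -1 values, and it falls with the previous item.
- **That the size can be read from counting result patterns**: 1 of 16 excluded under the literal rule, against 15 of 16 under an any-positive rule. Those are counts of logical possibilities, not probabilities, and say nothing about how many volunteers are affected.

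**Conclusion.** The point holds for exclusion 24 alone. As written, it is met only when both screens are positive at both visits, which conflicts with Table 1 and section 9.3. Exclusions 13, 25 and 28 soften the consequence but leave it to discretion.

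It is a drafting defect in an operative eligibility rule and should be corrected. It has no demonstrated effect on any analysis: the pharmacokinetic analysis is descriptive (section 11.9.4), and no sample size or other statistical figure moves. The number of volunteers affected cannot be estimated, because the documents give no frequency of positive screens.

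The conclusion rests on two assumptions: that criteria declared free of exceptions are to be applied as worded, and that the screens are meant to exclude on any single positive result, as their scheduling and stated purpose indicate.

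**What to change.** Reconcile exclusion 24 with Table 1 and section 9.3 by rewording it along these lines:

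*Any positive screen for drugs of abuse or for alcohol, at screening or on admission to the study center.*

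Exclusions 8 to 10 need no change on this account.

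The cost is one line of text. Both tests and both eligibility checks are already scheduled, so no procedure, visit or statistical figure changes. The small downside is that a volunteer may occasionally fail on Day -1 and a reserve volunteer will be needed.

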7.5.3. Discontinuation of subject, individual stopping criteria and withdrawal from the study

Subjects may be discontinued from the study in the following situations:

- Healthy subject decision. The healthy subject is at any time free to discontinue treatment, without prejudice to further treatment.
- Adverse event.
- Severe noncompliance to study protocol.
- Any significant and clinically relevant changes in the safety parameters (e.g., AEs, BP, pulse, ECG and laboratory assessments) making continuation in the study unjustified.

7.5.4. Premature termination of the study and stopping criteria

The study may be terminated prematurely if:

- The PI and the sponsor assess that the number and/or severity of AEs justify discontinuation of the study. For instance when there is at least 1 case of fatal SAE or

2 cases of other SAEs, in both situations considered related to the IMP by the investigator and the sponsor.

- The sponsor decides to discontinue the study.
- Data not known before become available and raise concern about the safety of IMP so that continuation would pose potential risks to the subjects.
- Premature termination of the study must be mutually agreed upon by the PI and the sponsor and must be documented. However, study results will be reported according to the requirements outlined in this clinical study protocol as far as applicable.

7.5.5. Replacement of subjects

Subjects who are withdrawn from the study will be replaced if the sponsor's responsible physician and the PI agree it is safe to do so.

Where a subject, who does not meet the selection criteria, is randomized in error and this is identified before IMP administration, the subject should be withdrawn from the study. If a subject is withdrawn prior to IMP administration, the subject will be replaced.

If a subject, who does not meet the selection criteria, has been dosed before the error is identified, the subject should be advised to continue safety assessments to ensure their safety. The PI will inform the AstraZeneca Lead Physician of the error and a joint decision will be made as to whether the subject should be replaced.

7.5.6. Total blood volume

The approximate total amount of blood to be collected from each subject in this study, excluding repeat samples, is summarized in [Table 2](#).

Table 2 Total Blood Volume

SC dosing	Volume per sampling	Number	Total
PK samples	4 mL	12	48 mL
ADA samples	4 mL	4	16 mL
Clinical Laboratory assessments*	6.5 mL	4	26 mL
Viral Serology	3.5 mL	1	3.5 mL
IGRA (QuantiFERON-TB GOLD)	3 mL	1	3 mL
Total			96.5 mL

PK = pharmacokinetic; ADA = anti-drug antibody; IGRA = Interferon Gamma Release Assay

*Includes hematology, serum clinical chemistry and urinalysis. See [Section 9.3.8](#).

IV dosing	Volume per sampling	Number	Total
PK samples	4 mL	13	52 mL
ADA samples	4 mL	4	16 mL
Clinical Laboratory assessments*	6.5 mL	4	26 mL
Viral Serology	3.5 mL	1	3.5
IGRA (QuantiFERON-TB GOLD)	3 mL	1	3 mL
Total			100.5 mL

PK = pharmacokinetic; ADA = anti-drug antibody; IGRA = Interferon Gamma Release Assay

*Includes hematology, serum clinical chemistry and urinalysis. See [Section 9.3.8](#).

Repeat blood samples may be collected for safety reasons. The maximum volume to be drawn from each subject must not exceed 500 mL.

8. TREATMENTS

8.1. Identity of the Investigational Medicinal Product

Details on the identity of the IMP are presented in [Table 3](#).

Table 3 Identity of the Investigational Medicinal Product

IMP:	Anifrolumab	Placebo
Supplier:	AstraZeneca	AstraZeneca
Formulation:	Concentrate for solution for SC injection or IV infusion	Concentrate for solution for SC injection or IV infusion
Strength/concentration:	150 mg/mL	Not applicable
Dose:	300 mg or 600 mg	Not applicable
Route of administration:	SC (abdomen ^a) or IV	SC (abdomen ^a) or IV
Specific device for drug administration, if applicable:	For Cohort 1 (300 mg): 27G ½” needle For Cohort 2 (300 mg): Latex-free IV infusion bags of normal 0.9% saline (100 mL size). Infusion lines should contain a low protein-binding 0.2 µm or 0.22 µm in-line filter. For Cohort 3 (600 mg): Syringe pump	For Cohort 1 (300 mg): 27G ½” needle For Cohort 2 (300 mg): Latex-free IV infusion bags of normal 0.9% saline (100 mL size). Infusion lines should contain a low protein-binding 0.2 µm or 0.22 µm in-line filter. For Cohort 3 (600 mg): Syringe pump
Regimen:	Single-dose	Single-dose
Special handling requirements:	The total in-use storage time from needle puncture for dose preparation to start of administration should not exceed 4 hours at room temperature or 24 hours at 2°C to 8°C (36°F to 46°F).	The total in-use storage time from needle puncture for dose preparation to start of administration should not exceed 4 hours at room temperature or 24 hours at 2°C to 8°C (36°F to 46°F).
Availability of the IMP:	IMP will be shipped after regulatory approval	NA

IMP = Investigational medicinal product; SC = Subcutaneous; IV = intravenous; mg = milligrams; mL = milliliters

^a Avoid 5 cm radius around umbilicus

AstraZeneca will provide detailed preparation, storage and handling instructions for each product and treatment. Details of the batch numbers will be included in the Trial Master File and the final CSR, as applicable.

8.2. Supply of Investigational Medicinal Product

The IMP will be manufactured in accordance with Good Manufacturing Practice (GMP) and will be supplied by AstraZeneca.

All drug products will be labelled in a double-blind fashion. Anifrolumab (MEDI-546) 150 mg and Placebo kits will be provided containing 2 vials/kit. Two vials of 150 mg or

2 vials of placebo. The vials will be labelled with a single panel label. Two labelled vials will be placed into an insert and into a carton labelled with a single panel label.

AstraZeneca will provide Anifrolumab (MEDI-546) and placebo vials. PAREXEL will provide IV infusion bags and labels to apply to IV bags after dose preparation.

If applicable, a technical agreement between PAREXEL and AstraZeneca will be in place to cover all pharmacy related activities, detailing roles and responsibilities prior to receipt of the IMP at the clinical unit.

If applicable, a release document signed by a legally authorized Qualified Person (QP) at PAREXEL will be placed in the appropriate section of the Trial Master File to document labeling.

8.3. Storage and Handling Procedures

The IMP will be stored in a secure facility under appropriate storage conditions. Details of storage conditions will be provided by AstraZeneca.

AstraZeneca will be permitted upon request to audit the supplies, storage, dispensing procedures and records.

8.4. Labelling

Labels will be prepared in accordance with GMP and local regulatory guidelines. The labels will fulfill GMP Annex 13 requirements and medical device directive for labelling.

8.5. Drug Accountability, Dispensing and Destruction

The IMP provided for this clinical study will be used only as directed in the clinical study protocol.

In accordance with GCP, the clinical unit will account for all supplies of the IMP. Details of receipt, storage, assembly/dispensing and return will be recorded.

All used and unused supplies of the IMP will be destroyed by PAREXEL at the end of the study. The certificate of delivery and destruction must be signed, in accordance with instruction by AstraZeneca. Destruction must not take place unless the responsible person at AstraZeneca has approved it.

8.6. Dose and Treatment Regimens

Subjects will receive a single dose of anifrolumab or placebo.

- Cohort 1: The first 10 subjects will be randomized to receive a single dose of either anifrolumab 300 mg or placebo (6 subjects anifrolumab 300 mg and 4 subjects placebo; delivered as 2 separate 1 mL SC injections).
- Cohort 2: The following 10 subjects will be randomized to receive a single dose of either anifrolumab 300 mg or placebo (6 subjects anifrolumab 300 mg and 4 subjects placebo; delivered as an IV infusion over 30 minutes).
- Cohort 3: After ≥ 6 subjects in Cohort 1 have been observed on the study for one week and the PI has deemed an acceptable safety profile, 10 subjects will be randomized to receive a single dose of either anifrolumab 600 mg or placebo (6 subjects anifrolumab 600 mg and 4 subjects placebo; delivered as 4 mL SC by infusion pump).

Restrictions are described in [Section 7.4](#). Data of subjects may be excluded from the PK analysis set as described in [Section 11.3.2](#).

Subcutaneous dosing will be given in the anterior abdominal wall, specifically avoiding the 5 cm radius around umbilicus.

The date and time of dosing will be recorded in the CRF, together with the location of the injection site for SC dosing. For IV dosing, the volume of the infusion together with the start and stop time will be recorded.

